7.3 Follow-up Participant Assessments

The event that starts the post-intervention data collection timing are as follows.

Acute Pain:

- Date of surgery (intervention and control arms)

Chronic Pain and Depression:

- Intervention arm: When the pharmacogenetics results are returned to the provider and deposited in the EMR
- Control arm: At date of DNA sample collection plus one week, where one week reflects the average time from sample collection to returning the results to the EHR
- Note: There will be variability in time the results are returned to provider and when genotype-guided therapy is delivered to the participant, time from results being available to the next provider-participant interaction (e.g. email, clinic visit, new prescription order, phone visit, etc.) will be recorded by study personnel.

Post intervention assessment collection may be done by the University of Florida College of PharmacyCall Center. The center agents will be trained survey collectors*, using an IRB approved telephone script. The collected survey responses will be entered into the study database. If preferred, the participant will have the option to complete the study follow-up survey by a URL link sent by text (to mobile phone) or email and captured in REDCap database

In the event that the call center is unable to reach a participant, local study coordinators may contact participants to facilitate completion of the follow-up surveys.

Data will be collected in the following timeframes*:

- Acute pain: 10 days, 1 month, 3 months, and 6 months post-surgery
- Chronic pain and depression: 1-month, 3 months, and 6 months post return of results for the intervention arm, and post baseline assessments for the control arm.

*See *MOP for call center agents and survey collection interval windows*

All Trials

PROMIS 43 – Adults (≥ 18 years of age) will complete a 43-question survey assessing well-being and sub domains: pain interference, physical function, sleep disturbance, social role and activities functioning, fatigue, anxiety, and depression.[32] This survey will be administered to adult participants at baseline, 1-month, 3-months, and 6-months post-surgery (acute pain), or baseline, 1-month, 3-months, and 6-months post return of results (chronic pain, depression).

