PROMIS prescription medication mis-use scale - A participant completed survey of prescription medication misuse over the past 3 months. The survey is comprised of 7 questions on a 5-point ordinal scale of never/rarely/sometimes/frequently/almost always or not at all/a little bit/somewhat/quite a bit/very much[33]. This survey will be administered at baseline, 3-months, and 6-months post-surgery.

PROMIS Item Bank v2.0 Mobility – A participant completed survey of the participant's level of difficulty in completing different physical activities such as standing unassisted, walking, and sprinting or activities that their health currently limits. The survey is comprised of 15 questions, each answered on a 5-point scale ranging from without difficulty to unable to do, or not at all through cannot do[34]. This survey will be administered at baseline, 10 days, 1-month, 3-months, and 6-months post-surgery to the adult participants.

PROMIS Pediatric Mobility – Short Form 8a – A participant completed 8 item survey of difficulty in completing different physical activities such as getting up from the floor, standing on tiptoes, and ability to do sports and exercises that their peers can complete [35]. The survey will be administered at baseline, 10 days, 1-month, 3-months, and 6-months post-surgery to the pediatric participants.

Acute pain specific health care utilization – A participant completed survey of hospital length of stay for the surgical admission, administered at 10 days post-surgery.

Opioid side effects – A participant completed survey of common opioid side effects experienced and the extent to which those side effects bothered the participant. This survey will be administered at baseline, 10 days, 1-month, 3-months, and 6-months post-surgery.

Opioid persistence - Whether or not the participant had an opioid prescription refill 90 – 180 days post-surgery. This survey will be administered to participants at 6 months post-surgery.

Chronic Pain:

PROMIS pain intensity scale – A participant completed 3-question survey of average pain over the last 7 days, worst pain over the last 7 days, and current pain. Each question is on a 1-5 integer scale, the

higher the value, the more intense the pain. This survey will be administered at baseline, 1 month, 3 months, and 6 months post return of results.

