7.8 Data Collection from the Electronic Health Record

Data collected from the local EHR will include prescription information and encounters including clinic visits, hospitalizations, and emergency department visits and associated diagnoses for the study interval time-zero through six-month follow up. Sites will extract data using prespecified programmatic algorithms, site-developed algorithms, and/or manual chart abstractions. EHR query results will be sent to the IGNITE PTN CC via secure data transfer and formatted for consistency across sites. Details for the EHR elements and transfer process will be provided in the MOP.

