7.9 Data Collection from CMS and State Medicaid Agencies

Medicare and Medicaid claims data from CMS and state Medicaid agencies will be used to assess health care utilization, costs, and medications among participants covered by either Medicare or Medicaid. Claims made in the period of 12 months prior to surgery (acute pain) or return of results (chronic pain, depression) through 6 months following those events will be collected. See Section 9 and the MOP for additional details. Schedule of Activities and Timeframe for Collection of Endpoints

Table 8. Data collection schedule

Data collection schedule, method of data collection, and timing

Outcome	Data source/instrument	Baseline	10 d ± 3 d	1 mo. ± 7 d	3 mo. ± 14 d	6 mo. ± 14 d
Pain Assessments						
Pain intensity	PROMIS Pain intensity scales	AP, CP	AP	AP, CP	AP, CP*	AP, CP
Pain intensity	PROMIS Numeric Rating Scale - Pain Intensity (NPRS)	AP	AP*	AP	AP	AP
Daily opioid dose & type of opioid use	Average daily mg morphine equivalents (MED) since discharge use of opioids: tramadol/ codeine vs others		AP*	AP		
Opioid use disorder	PROMIS - Prescription pain medication misuse subscale	AP, CP			AP, CP	AP, CP
Mobility	PROMIS mobility	AP	AP	AP	AP	AP
Depression Assessments						
Depressive state	PROMIS Emotional Distress - Depression 8b survey	CP, D		CP, D	CP, D*	CP, D
Depressive state	Patient Health Questionnaire-8 depression scale	D			D	D
Participant Medications						
Assessment of prescriptions	Custom survey/EHR	AP, CP, D	AP		CP, D	
Assessment of filled prescriptions	Medicaid and Medicare billing records for 12 months prior to time 0 through 6 months after time 0			AP, CP, D		

Adherence	Voils Medication Adherence		D		D	D	D
SSRI AE Survey	Custom survey		D		D	D	D
Opioid side effect survey	Adapted medication side effect survey (SPACE)		AP, CP	AP	AP, CP	AP, CP	AP, CP
Opioid persistence	Custom survey						AP
Participant Actions							
Interaction with provider	Participant visits				CP, D		
Interaction with test result	Custom survey						AP, CP, D
Quality of life and well being							
Past Medical History	Participant visits/custom survey		AP, CP, D				
Well-being	PROMIS43/PROMIS Peds37		AP, CP, D		AP, CP, D	AP, CP, D	AP, CP, D
Healthcare Utilization and Costs							
Medicare/Medicaid billing records	Medicaid and Medicare billing records for 12 months prior to time 0 through 6 months after time 0				AP, CP, D		
LoS	LoS for index admission			AP			

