reasons, we will conduct covariate-adjusted repeated measures mixed models that will account for differences in baseline characteristics that differ between the Intervention – CYP2D6 PM or UM or CYP2C19 UM, RM or PM subgroup and the Control – CYP2D6 PM or UM or CYP2C19 UM, RM or PM subgroup. Potential baseline characteristics may include age, sex, income, education, insurance, medical conditions. We will select the appropriate covariance matrix (e.g. compound symmetry, autoregressive, unstructured, or other covariance structure) based on the data.

Difference within the NM group. In the control arm participants, we will compare depression scores and depression control in participants with a CYP2D6 activity score $>0.75 - 1$ to participants with an activity scores $>1-2$ using a two-sided two-sample t-test or Mann Whitney test, as appropriate, with a type 1 error of 0.05. Additionally, we will use linear regression to adjust for differences in baseline characteristics

Cost Effectiveness

Healthcare costs: In the Medicare fee-for-service or Medicaid enrollees, log-transformed overall expenditures (between index visit and 6 months follow-up) will be compared using a 2-sample t-test between the study arms (after ensuring that the variances in the log-scale are equal). Alternatively, cost comparisons will be made using appropriate regression models such as generalized linear models. For all participants, regardless of insurance type, we will estimate and aggregate participant-reported healthcare utilization during follow-up and assign cost for each item based on unit weighted mean cost estimates from the Medicare/ Medicaid data.

Within the Medicare/Medicaid population, we will compare estimated cost differences between genotype-guided and usual care based on billing records versus participant report to further validate the cost comparisons for the entire population. Cost for the index hospitalization for surgery participants will not be included in the cost estimate, but we will compare length of stay between groups as reference for hospitals regarding potential cost savings in capitation-based reimbursement schemes. All costs will be converted to 2021 \$US using the chain-weighted Consumer Price Index (CPI).

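### Index length of stay has one named source, a participant survey 7 to 13 days after surgery, and no rule for stays still in progress

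*Combined protocol and SAP*

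**What the plan says.** Section 7.3 (Acute Pain) defines the acute-pain utilization item as "A participant completed survey of hospital length of stay for the surgical admission, administered at 10 days post-surgery". Table 8 has a matching row, "LoS for index admission", marked for acute pain at one follow-up visit, the 10-day visit with its ±3-day window. In Acute Pain, follow-up time runs from the date of surgery in both arms (section 7.3).

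Section 10.6 (Cost Effectiveness) leaves what the surgical admission costs out of its cost totals and gives the stay a separate role: "we will compare length of stay between groups as reference for hospitals regarding potential cost savings in capitation-based reimbursement schemes". Length of stay is therefore the planned measure of the index admission itself.

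Other sources span the same stay but are not assigned to it. Section 7.8 has sites extract from the EHR "encounters including clinic visits, hospitalizations, and emergency department visits and associated diagnoses for the study interval time-zero through six-month follow up". Section 7.9 collects Medicare and Medicaid claims from 12 months before surgery to 6 months after, for enrollees in those programmes only. Section 9.1 says self-reported major cost drivers will be checked against claims where possible.

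Length of stay has no entry in the data element definitions (section 11.2). The multiple-imputation rule in section 10.8 is stated for primary and secondary analyses, and length of stay is neither.

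**The concern.** A participant who has not been discharged when surveyed has no completed stay to report. No later survey asks for the index stay again: the 1-, 3- and 6-month items in Table 8 cover visits, rehabilitation or long-term care days, and home healthcare days. Eligible operations include spine, open abdominal and cardiothoracic surgery (section 5.1), so some stays longer than a week are plausible.

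The survey therefore loses information in the upper tail, which contributes disproportionately to mean bed-days. The cut-off also differs between participants by up to six days, according to when each is reached. At stake is the comparison offered to hospitals as a guide to savings. If genotype-guided prescribing shortened stays proportionally, the survey-based difference in means would be too small.

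**Working it through.** **Window.** 10 − 3 = 7 and 10 + 3 = 13, so the survey falls on days 7 to 13 after surgery.

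**Plan's own figure.** There is none to reproduce. The documents give no mean, SD, sample size or power for length of stay. Everything below is assumed and shown as a range.

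**Model.** Stays are log-normal with median M and log SD s, counted from surgery. The survey is on day c. One arm's stays are shorter by a fixed proportion. With z = ln(c/M)/s:

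- true mean: μ = M·exp(s²/2)
- share unfinished at the survey: p = 1 − Φ(z)
- part of the mean from finished stays: B = μ·Φ(z − s)
- mean if unfinished stays are dropped: B/(1 − p)
- mean if they are recorded as days so far: B + c·p

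**Worked case: M = 3, s = 0.8, c = 10, 15% reduction.**

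- Control: μ = 3·exp(0.32) = 4.131; z = 1.505; p = 0.066; B = 3.138. Dropped: 3.138/0.934 = 3.36. Days so far: 3.138 + 0.662 = 3.80.
- Intervention, median 0.85 × 3 = 2.55: μ = 3.512; z = 1.708; p = 0.044; B = 2.873. Dropped: 3.00. Days so far: 3.31.
- Difference: true 4.131 − 3.512 = 0.62; dropped 0.36; days so far 0.49.

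**Three cases, survey on day 10, 15% reduction.** The shares are for the longer-stay arm.

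| Median, log SD | Stays unfinished | Bed-days in those stays | True difference (days) | If dropped | If days so far |
|---|---|---|---|---|---|
| 2, 0.7 | 1% | 5% | 0.38 | 0.33 | 0.37 |
| 3, 0.8 | 7% | 24% | 0.62 | 0.36 | 0.49 |
| 5, 0.7 | 16% | 39% | 0.96 | 0.41 | 0.63 |

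**Effect of the window.** Median 4, log SD 0.7, with a 10% reduction; the true mean is 5.11 days and the true difference 0.51 days.

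| Survey day | Stays unfinished | Mean if dropped | Mean if days so far | Difference if dropped | Difference if days so far |
|---|---|---|---|---|---|
| 7 | 21.2% | 3.50 | 4.24 | 0.18 | 0.29 |
| 10 | 9.5% | 4.12 | 4.68 | 0.27 | 0.39 |
| 13 | 4.6% | 4.49 | 4.88 | 0.34 | 0.44 |

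Under this model the mean is understated and the difference is closer to zero with either handling. Dropping is worse than recording days so far, and an early survey is worse than a late one.

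**The case against.** A reader might infer that the longest stays cannot be scored and fall out of the comparison. The documents do not say so. They are silent, and a stay in progress could be entered as days so far, which loses less. The EHR extract covers hospitalizations from the day of surgery for participants generally, and claims cover Medicare and Medicaid enrollees, so final lengths may be recoverable. This objection stands: the gap is an unassigned source and a missing rule, and loss of data is not established.

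A reader might also infer that any difference between arms is pulled towards zero. That is shown only for a proportional reduction and a comparison of means. Arms that differed in opposite directions in short and long stays could behave otherwise. Section 10.6 names no statistic for length of stay, and a median that counted unfinished stays as long would be unaffected while it lay below the cut-off. This also stands, and the claim is limited accordingly.

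Third, detail is deferred: cost analyses to the study SAP (section 10.6), EHR elements to the MOP (section 7.8). Those documents are not available here and may contain a rule. Even so, this protocol names the survey as the source, in both section 7.3 and Table 8, when a source without a day-10 cut-off is already being extracted.

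**Conclusion.** The point holds as a minor one. The single named source for index length of stay is cut off between day 7 and day 13, with no stated handling of stays in progress. Taken from the survey alone, mean stay is understated whenever some stays outlast the survey, and for a proportional effect the difference in means is attenuated.

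The size rests entirely on assumed log-normal stays. At a median of 2 days almost nothing is lost; at a median of 5 days roughly a third to over half of the true difference disappears (0.63/0.96 = 66% kept with days so far, 0.41/0.96 = 43% kept if dropped). The case mix and stay lengths needed to place the trial on that range are not in the documents.

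A reader might carry this over to the economic results. The text does not support that: index hospitalization cost is excluded from the cost estimate by design, so the cost estimate and the ICER are untouched. So are the primary and secondary endpoints. Only the exploratory length-of-stay comparison is affected.

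**What to change.** In section 7.3, Table 8 and section 10.6:

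1. Name the EHR hospitalization record for the index admission, extracted under section 7.8 from time zero, as the source of length of stay.
2. Confirm that the extract includes admission and discharge dates. Section 7.8 lists encounter types and diagnoses but does not mention those dates.
3. Use the day-10 survey only where the EHR record is missing.
4. Treat any survey-only stay that has not ended as right-censored at the survey date. It should not enter a mean as if it were complete.

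The enrolling site's EHR should usually hold the admission, because section 6.3 allows withdrawal of participants operated on in a different healthcare system. The cost is wording changes plus a small amount of EHR extraction and cleaning. No new survey question is needed.

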7.4 Specimen Collection

DNA sample collection can be whole blood by venipuncture, saliva, buccal swab, or mouthwash, whichever is most appropriate for the site or study participant preference. The sample collection can occur in person or by mailed kits after consenting.

Once sample collection is completed, participants are randomized to a trial Control or Intervention arm. All DNA sample types and collection processes are detailed in the MOP.

7.5 Specimen Transfer and Genetic Testing Procedures

All collected specimens will be clearly marked with two patient identifiers (CLIA requirement). Samples from the Intervention arm participants will be processed, using analytically validated PGx testing procedures (see Table 1 for gene and variant list). For Control arm samples, designated laboratories will either extract DNA after sample receipt, and store the DNA for later analysis or store the sample and extract DNA after the Control participant has completed the 6-month follow-up assessment. After the Control participant has completed the 6-month follow-up assessment, Control Arm samples will be processed using analytically validated procedures. Details of sample storage and transport will be presented in the MOP.

7.6 Return of Results

The designated laboratory will transfer participant genetic testing results to the EHR. Genetic results will be imported into the study database. Providers will be notified of participant results via standard site-specific laboratory return of results methods, a static report/consult note with interpretation and treatment recommendations, and, where possible, a CDS within the EHR as described in Sections 7.1 and 7.7.

After their participation in the trial is complete, the PGx testing results will be actively returned to the participants. The PGx testing results that are returned to the participant will follow current FDA guidance.

7.7 Clinical Decision Support Systems

Providers will be notified of participant results via standard site-specific laboratory return of results methods, a static report/consult note with both interpretation and treatment recommendations, and, where possible, a just in time alert within the electronic health system. Sites will work with their institutional information technology departments to set up provider alerts for actionable PGx phenotypes when a relevant opioid or SSRI medication is ordered. Provider alerts will indicate the participant's genetic results, the predicted phenotype (e.g. efficacy of various opioid or SSRIs), and prescribing recommendations.

Continuing on the health IT collaborative efforts established in IGNITE I through CDSKB (<http://cdskb.org>), all participating sites will seek to harmonize their CDS logic, recommendations, and provider alerts using a framework of required and optional elements for both the static report and the just in time alert. However, due to the pragmatic nature of the trial, the many involved research sites, and variations in local CDS policies, it is anticipated that there will be differences in CDS implementation details, but all sites will ensure that providers are alerted to the PGx test results and associated significance. Details of the alerts will be provided in the MOP.

7.8 Data Collection from the Electronic Health Record

Data collected from the local EHR will include prescription information and encounters including clinic visits, hospitalizations, and emergency department visits and associated diagnoses for the study interval time-zero through six-month follow up. Sites will extract data using prespecified programmatic algorithms, site-developed algorithms, and/or manual chart abstractions. EHR query results will be sent to the IGNITE PTN CC via secure data transfer and formatted for consistency across sites. Details for the EHR elements and transfer process will be provided in the MOP.

7.9 Data Collection from CMS and State Medicaid Agencies

Medicare and Medicaid claims data from CMS and state Medicaid agencies will be used to assess health care utilization, costs, and medications among participants covered by either Medicare or Medicaid. Claims made in the period of 12 months prior to surgery (acute pain) or return of results (chronic pain, depression) through 6 months following those events will be collected. See Section 9 and the MOP for additional details. Schedule of Activities and Timeframe for Collection of Endpoints

Table 8. Data collection schedule

Data collection schedule, method of data collection, and timing

Outcome	Data source/instrument	Baseline	10 d ± 3 d	1 mo. ± 7 d	3 mo. ± 14 d	6 mo. ± 14 d
Pain Assessments						
Pain intensity	PROMIS Pain intensity scales	AP, CP	AP	AP, CP	AP, CP*	AP, CP
Pain intensity	PROMIS Numeric Rating Scale - Pain Intensity (NPRS)	AP	AP*	AP	AP	AP
Daily opioid dose & type of opioid use	Average daily mg morphine equivalents (MED) since discharge use of opioids: tramadol/ codeine vs others		AP*	AP		
Opioid use disorder	PROMIS - Prescription pain medication misuse subscale	AP, CP			AP, CP	AP, CP
Mobility	PROMIS mobility	AP	AP	AP	AP	AP
Depression Assessments						
Depressive state	PROMIS Emotional Distress - Depression 8b survey	CP, D		CP, D	CP, D*	CP, D
Depressive state	Patient Health Questionnaire-8 depression scale	D			D	D
Participant Medications						
Assessment of prescriptions	Custom survey/EHR	AP, CP, D	AP		CP, D	
Assessment of filled prescriptions	Medicaid and Medicare billing records for 12 months prior to time 0 through 6 months after time 0			AP, CP, D		

Adherence	Voils Medication Adherence		D		D	D	D
SSRI AE Survey	Custom survey		D		D	D	D
Opioid side effect survey	Adapted medication side effect survey (SPACE)		AP, CP	AP	AP, CP	AP, CP	AP, CP
Opioid persistence	Custom survey						AP
Participant Actions							
Interaction with provider	Participant visits				CP, D		
Interaction with test result	Custom survey						AP, CP, D
Quality of life and well being							
Past Medical History	Participant visits/custom survey		AP, CP, D				
Well-being	PROMIS43/PROMIS Peds37		AP, CP, D		AP, CP, D	AP, CP, D	AP, CP, D
Healthcare Utilization and Costs							
Medicare/Medicaid billing records	Medicaid and Medicare billing records for 12 months prior to time 0 through 6 months after time 0				AP, CP, D		
LoS	LoS for index admission			AP			
ED/urgent care & inpatient visits	Participant reported visits				AP, CP, D	AP, CP, D	AP, CP, D
Outpatient visits	Participant reported primary care & pain clinic visits				AP, CP, D	AP, CP, D	AP, CP, D
Outpatient visits	Long-term care or in-patient rehab days, home healthcare days				AP	AP	AP
Productively Loss	Survey of lost work time and income				AP, CP, D	AP, CP, D	AP, CP, D

Abbreviations: CP – chronic pain, AP – acute post-surgical pain, D-depression, ED – emergency department, EHR – electronic health record; LoS – length of stay; PT – physical therapy

*Denote primary endpoints

